The results of this study may help synthesize complex intraoperative clinical information and unveil novel therapeutic strategies. Derived from data from the QEII Hospitals, the results would be directly applicable to the care of Nova Scotians. The models may lead to the creation of objective risk stratification scores calculated at the end of surgery, to identify high risk patients for increased postoperative follow-up and monitoring. Moreover, if models created using machine learning perform well, machine learning may be used more frequently to reveal the patterns within complex, large perioperative datasets. Hemodynamics are potentially modifiable risk factors. Future research includes prospective studies on whether targeted hemodynamic goals, increased postoperative follow-up of high-risk patients, and real-time machine learning precision medicine could improve outcomes after surgeries.

Specific aims

1. To use machine learning techniques to investigate systematically intraoperative hemodynamic predictors of postoperative 30-day all-cause mortality (primary outcome) and major in-hospital morbidity. Hemodynamic predictors to be studied are blood pressure, heart rate, oxygen saturation, end-tidal carbon dioxide, and medications to adjust blood pressure. Please see “Outcomes” section below for full list of secondary outcomes.
2. To evaluate performance of machine learning models created and compare the performance of the best model to the Surgical Apgar Score.

Hypothesis

Controlling for other predictors, the durations of mean arterial pressure (MAP) <65mmHg, heart rate <60 or >100 beats per minute (BPM), hemodynamic medications use, oxygen saturation (SpO₂) <88%, and end-tidal carbon dioxide (EtCO₂) <30 or >45 will be associated with postoperative 30-day all-cause mortality (primary hypothesis) and 30-day major in-hospital morbidity (secondary hypothesis). Note that blood pressure, heart rate, vasopressors and

inotropic medications, oxygen saturation, and end-tidal are considered key indicators of hemodynamics. We have chosen conventional ranges commonly used in practice, and will perform sensitivity analysis of different definitions of each hemodynamic variable.

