Heart rate	Since both fast and slow heart rate may be harmful and there is no universal definition of abnormal heart rate under anesthesia, we will model using a variety of methods. 
 1. Maximum change (BPM) from preoperative heart rate (positive and negative) 2. Relative change (%) from preoperative heart rate (positive and negative) 3. Maximum pulse variation (maximum heart rate minus minimum heart rate) 4. Longest single episode (minutes) a) below 60, and b) above 100BPM 5. Cumulative duration (minutes) a) below 60, and b) above 100BPM
Use of hemodynamic medications (i.e. special medications for blood pressure)	
 1. Vasopressor/inotrope use (yes vs. no): phenylephrine, norepinephrine, epinephrine, vasopressin, dobutamine, or milrinone 2. Infusion of any vasopressor/inotropes above (yes vs. no) (identified by unit of weight over time) 3. Phenylephrine/ephedrine bolus (yes vs. no) (identified by unit of weight only) 4. Vasodilator use (yes vs. no): labetalol, esmolol, nitroglycerin, nitroprusside 5. Infusion of any vasodilator above (yes vs. no) (identified by unit of weight over time)
Oxygen saturation by pulse oximetry: SpO₂	
 1. Longest single episode (minutes) below a) 88, and b) 90% 2. Cumulative duration (minutes) below a) 88, and b) 90%
End-tidal (i.e. exhaled) Carbon dioxide: EtCO₂	
 1. Longest single episode (minutes) a) below 30, and b) above 45mmHg 2. Cumulative duration (minutes) a) below 30, and b) above 45mmHg

II. Outcomes

Primary: 30-day all-cause postoperative mortality (binary)

Secondary:

1. Major 30-day in-hospital morbidity, both in terms of the individual category (yes/no), and an overall composite (i.e. yes for any of the 6 categories vs. no). We have included major morbidity outcomes where increased monitoring would be beneficial, using International Statistical Classification of Diseases (ICD) 10 codes and based on published protocol on patient safety indicators (27).
 1. Cardiac: composite of acute myocardial infarction, cardiac arrest, ventricular tachycardia, congestive heart failure, pulmonary edema, complete heart block, shock excluding septic shock
 2. Respiratory: composite of pneumonia, pulmonary embolism, acute respiratory failure, respiratory arrest, Mechanical Ventilation \geq 96 hours
 3. Acute Kidney Injury
 4. Cerebrovascular: composite of strokes and transient ischemic attacks

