			
Comorbidity covariates: We need the following DXCODE (with “DXTYPE[1-n] = 1”, OR “DXTPRE[1-n] = 2 AND DXPRE[1-n] = 5”, OR “DXTYPE[1-n] = 3 AND DXPRE[1-n] = 5”, OR “DXTYPE[1-n] = M AND DXPRE[1-n] = 5”) within 3 years before PDATE: Disease categories for RCRI (please see “RCRI”); hypertension (I10-I15), COPD (I27.8, I27.9, J40.x–J47.x, J60.x–J67.x, J68.4, J70.1, J70.3), Obesity (E66)
 
Postoperative outcomes: We need the following DXCODE (with “DXTYPE [1-n]=2” Excluding “DXTYPE [1-n]=2 AND DXPRE [1-n]=5”, OR “DXTYPE [1-n]=3” excluding “DXTYPE [1-n]=3 AND DXPRE [1-n]=5”, OR “DXTYPE[1-n] = M AND DXPRE[1-n] = 6”) to include into model as individual, categorical, and composite secondary outcome:
 
Cardiac: acute myocardial infarction (I21 to I22, I24), cardiac arrest (I46.0, 146.1, I46.9), ventricular tachycardia (I47.2), shock (R57, T81.1) excluding septic shock (R57.2), congestive heart failure (I50.0, I50.1, I50.9), pulmonary edema (J81), complete heart block (I44.2)
 
Respiratory: pneumonia (J13 to J18, J69.0, J69.8, J95.4), pulmonary embolism (I26), acute respiratory failure (J95.1, J95.2, J96.0), respiratory arrest (R9.2)

--	--	--	--

				
Cerebrovascular: strokes and transient ischemic attacks (I60 to I69, G45)
 
Delirium (F5)
 
Acute kidney injury (N17)
 
Septic shock (R57.2)

CIHI DAD	DXPRE [1-n]: diagnosis prefix	Patient	Jan 1, 2010 to Dec 31, 2017 (3 years before and including 30 days after date of surgery)	
To categorize the type of the corresponding DXCODE (please see above):
 
C = Cause of death Q = Query Diagnosis/Etiology 5 = Comorbidity arose before qualifying intervention 6 = Comorbidity arose during or after qualifying intervention 8 = Palliative Care

CIHI DAD	DXTYPE [1-n]: diagnosis type	Patient	Jan 1, 2010 to Dec 31, 2017 (3 years before and including 30 days after date of surgery)	
To categorize the type of the corresponding DXCODE (please see above):
 
M = Most Responsible Diagnosis 1 = Pre-admit comorbidity 2 = Post-admit comorbidity 3 = Secondary Diagnosis

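### Coded morbidity keeps events that arose during surgery, so in the cardiac category and the overall composite part of the outcome can be the same event that generated the intraoperative exposures

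*Combined protocol and SAP*

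**What the plan says.** The Hypothesis section relates "the durations of mean arterial pressure (MAP) <65mmHg, heart rate <60 or >100 beats per minute (BPM), hemodynamic medications use", together with low oxygen saturation and abnormal end-tidal carbon dioxide, to "30-day major in-hospital morbidity (secondary hypothesis". Table 1 defines the drug exposure as "Vasopressor/inotrope use (yes vs. no): phenylephrine, norepinephrine, epinephrine, vasopressin, dobutamine, or milrinone". The hemodynamic variables are measured over the monitored case (Data processing and artifact removal).

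The Outcomes section puts these events, among others, in the cardiac category: "ventricular tachycardia, congestive heart failure, pulmonary edema, complete heart block, shock excluding septic shock". It also lists cardiac arrest. The DXCODE row of Appendix 1 gives the codes, including "ventricular tachycardia (I47.2), shock (R57, T81.1) excluding septic shock (R57.2". The Appendix 1 row for the heart resuscitation flag places that flag in the cardiac category, and the composite morbidity row includes it without any timing condition.

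The DXCODE row heads these codes as postoperative outcomes and selects them as follows:
- Type 2 (post-admission) and type 3 (secondary) diagnoses count unless they carry prefix 5, meaning they arose before the intervention.
- Type M (most responsible) diagnoses count if they carry prefix 6, which the DXPRE row defines as "6 = Comorbidity arose during or after qualifying intervention".

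**The concern.** A filter that drops only prefix 5 cannot tell an event in the operating room from one on the ward. A shock or arrest during surgery would be expected to produce minutes of low pressure, an abnormal heart rate and vasopressor treatment. It can also be coded as an outcome. For that patient, exposure and outcome describe the same event, and the association says nothing about what happens later.

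Two uses of the results are exposed to this. The Hypothesis section tests association with morbidity, and Evaluating model performance plans measures of association between hemodynamic thresholds and the secondary outcomes. Patients with intraoperative shock or arrest would be expected to cluster at the lowest pressures, so a threshold comparison could be distorted as well as a single odds ratio. In addition, the Outcomes section says the morbidity events were chosen because closer monitoring would help, and an event that is over before the patient leaves the operating room does not fit that purpose.

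**Working it through.** **Plan's own figure.** The only sizing figure concerns the primary outcome: 0.017 × 24,000 = 408 deaths, and 408 / 10 = 40.8, which the plan gives as 41 predictors. It reproduces, and this point does not rest on it. The plan gives no morbidity rate.

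**Step 1: does an intraoperative event pass the filter?**
- Type 2 or 3 with prefix 6, or with no prefix: kept, because only prefix 5 is excluded.
- Type M with prefix 6: kept.
- Resuscitation flag: kept, because no prefix or time applies to it.

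**Step 2: can another requested variable remove it?** The follow-up window is set by procedure date, admission date and discharge date (Appendix 1, PDATE, Admit-date and Discharge_date rows). None of these dates the diagnosis. The plan separates intraoperative from postoperative timing for deaths (Cohort characteristics; secondary outcome 5) and identifies ICU admission on or before the procedure date. It has no equivalent step for morbidity.

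**Step 3: does a planned analysis expose it?** The sensitivity analyses vary the hemodynamic definitions, and the subgroups are patient and procedure groups. The Limitations section mentions misclassification and ascertainment bias only in general terms.

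**Step 4: illustration of size.** All inputs are assumptions: no true effect, background risk 0.10 in everyone, a proportion p of patients exposed, and a proportion s of all patients with a coded intraoperative event, all of them exposed.

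Risk if exposed = 0.10 + (s/p) × 0.90. Risk if unexposed = 0.10, with odds 0.10/0.90 = 0.1111.
- s = 0.005, p = 0.30: 0.10 + 0.01667 × 0.90 = 0.1150; odds 0.1150/0.8850 = 0.1299; OR = 0.1299/0.1111 = 1.17.
- s = 0.005, p = 0.20: 0.10 + 0.025 × 0.90 = 0.1225; odds 0.1225/0.8775 = 0.1396; OR = 0.1396/0.1111 = 1.26.

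Of the 35,000 patients in the estimated cohort, s = 0.005 is 175 patients.

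**Step 5: second parameterisation.** Let q be the coded outcome rate, e the exposure prevalence and f the share of coded events that are intraoperative and exposed. Then P(E|Y) = f + (1 − f)e and P(E|no Y) = (e − q × P(E|Y))/(1 − q), and the OR is the ratio of the two odds. Over q = 5–15% and e = 20–60%, again with no true effect:

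| f | Apparent OR |
|---|---|
| 0 | 1.00 |
| 2% | 1.04–1.12 |
| 5% | 1.09–1.32 |
| 10% | 1.20–1.70 |

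The inflation disappears when no coded event is intraoperative, as it should.

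**The case against.** The strongest reply has several parts.

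- **Wording.** The hypothesis claims association and speaks of in-hospital morbidity; the postoperative label on these codes is an Appendix heading. This stands, but the mixed timing still has to be stated, because the results will be read as predicting later events.
- **Exposure and outcome are not the same variable.** A reader might infer that hypotension, arrest and arrhythmia are each both exposure and outcome. The documents do not support that. Hypotension is not an outcome code (only coded shock is), and arrest and arrhythmia are not listed exposures. The overlap runs through their vital signs and drug treatment.
- **Artifact rules.** Heart rates above 170 or below 30, saturation below 50%, end-tidal carbon dioxide below 5, implausibly narrow pulse pressures and abrupt systolic changes are removed. This trims part of the signature. Low-pressure minutes outside those rules, heart rates of 30–59 and 101–170, and drug use remain.
- **Adjustment and model form.** Durations enter as splines, and blood loss, transfusion and lowest hemoglobin are candidate covariates. They may absorb some hemorrhagic shock, so the crude odds ratios above are not forecasts. They do not change what the outcome counts.
- **Separate reporting is partly planned.** Individual, category and composite outcomes are all to be modelled, so a reader could set the cardiac results beside the other categories. That does not give a composite free of the overlap.
- **Large effects.** With s = 2% the Step 4 formula gives odds ratios of 1.71 (30% exposed) and 2.11 (20% exposed). But 2% of 35,000 is 700 patients, more than the 0.017 × 35,000 = 595 deaths implied by the plan's mortality estimate. Nothing in the documents supports a frequency that high.
- **End-of-surgery score.** A reader might also infer that the model's purpose is defeated. The score is described only as something that may follow, and model building targets mortality.

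**Conclusion.** The concern holds in a limited form. By the plan's own definitions, intraoperative shock, arrest, ventricular tachycardia, complete heart block and resuscitation can count as morbidity while their hemodynamic consequences count as exposure. No requested variable, planned sensitivity analysis or stated limitation deals with this. The direction is toward inflated associations, and the reach is the cardiac category and the overall composite of the secondary hypothesis.

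The documents do not support extending this to the primary outcome, since 30-day mortality comes from the date of death and does not use the prefix rule. Nor do these codes enter the other five morbidity categories, and within the composite the circularity is partial.

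The size is unknown. An odds ratio of about 1.17 to 1.26 in the absence of any effect assumes a 10% background risk, 20–30% of patients exposed, coded intraoperative events in 0.5% of patients, all of them exposed, and no covariate adjustment. How often intraoperative events receive these codes depends on coding practice that the documents do not describe.

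**What to change.** 1. Keep the cardiac category and the composite as written.
2. Pre-specify a second version of each that omits non-septic shock (R57 other than R57.2, and T81.1), cardiac arrest, ventricular tachycardia, complete heart block and FLAG_HEARTRESUS. Report each omitted component on its own line. The flag has to be on the list, because otherwise intraoperative arrests would re-enter through it.
3. State in advance that hemodynamic exposures will be said to predict postoperative cardiac or composite morbidity only if the association holds in the second version.
4. State in the Outcomes and Limitations sections that the coded outcome includes events during surgery.
5. Do not infer intraoperative events from the exposure vital signs, because outcome status would then depend on the exposure data. Do not recode patients with such events as event-free in the as-written version. In the second version the components are dropped for everyone, whatever their timing.

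The cost is two more derived variables from codes and a flag already requested. The second version has fewer events and omits genuine postoperative shock and arrest. A patient whose only event is an omitted one is a non-case there, which can pull the association down. Those events stay in the as-written version and the separate lines, which is why both versions should be reported.

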 5. Delirium
 6. Septic Shock
2. Postoperative ICU admission (yes/no)
3. Prolonged Postoperative Length of Stay (LOS) (greater than vs. less than or equal to CIHI Expected Length of Stay (ELOS) as assigned by the Case Mix Grouping) [note that the LOS includes the day of surgery]
4. Hospital readmission within 30 days (yes/no)
5. Intraoperative mortality (yes/no)
6. Days alive and out of hospital at 30 days postoperatively (28)

III. Other predictors included into model

The following potential perioperative predictors will be evaluated as covariates during model building. Statistically significant predictors will be retained in the model.

Table 2. Other predictors

Preoperative	
 1. Demographics: age on date of surgery, sex, obesity (body mass index>30) 2. Indicators of preoperative comorbidities: since no comorbidity score has perfect performance, a variety of models will be evaluated and the most significant predictive score will be retained in the model. 
 • American Society of Anesthesiologist class • RCRI score(29), and specific components via ICD codes (history of ischemic heart disease, congestive heart failure, cerebrovascular disease, diabetes, chronic kidney disease, and CCI and Case Mix Group codes of suprainguinal vascular, intraperitoneal, or intrathoracic surgery) using previously published methods (30)(31) • Elixhauser comorbidity index (32) and Charlson Comorbidity Index (33): calculated using diagnoses from the previous three years according to standard algorithm by HDNS. Reported as both total score and individual categories • Hospital Frailty Risk Score (34): based on ICD codes • Preoperative blood pressure: ICD diagnosis of hypertension and by measured blood pressure • Preoperative heart rate: Innovian and HSM • Chronic Obstructive Lung Disease (ICD code): since it may affect the interpretation of results of SpO₂ and EtCO₂ 3. Indicators of surgical complexity 
 • CIHI DAD Case Mix Group (CMG) class (also contains categories that include medical complexity) • Main Surgical Service • Procedural Index for Mortality Risk (PIMR) (35): according to CCI • Procedure: CCI codes • Preoperative ICU admission • Emergency surgery: as determined by DAD Method of Entry = emergency department or transferred from another institution)

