The performance of all models created will be evaluated in the validation set as part of internal validation using the same metrics of discrimination, calibration, and risk reclassification, and compared to the Surgical Apgar Score. Since there will likely be significant class imbalance and ROC curves may overestimate model performance, for each model, precision and recall curves (PRC), F score, average precision, and AUC will also be reported and compared. The best performing model will also be used to analyze for predictors for secondary outcomes. Sensitivity (recall, true positive rate), specificity, positive predictive value (precision), G-mean, negative predictive values, False Discovery Rates (FDR), optimism, and measures of association of hemodynamic thresholds for primary and secondary outcomes will be computed. Bayesian network causal inference analysis may be performed, to help increase interpretability.

Sensitivity and subgroup analysis

Sensitivity analysis will be performed for different definitions of hemodynamic derangements. Subgroup analysis will be performed based on age, sex, high preoperative risk (most significant indicator of preoperative comorbidity in Table 2, based on final model), RCRI, frailty (HFRS), preoperative hypertension, a select list of intermediate-high risk, gender-neutral elective surgery (please see Appendix – RCRI Protocol Table 1), emergency surgery, and type of anesthesia.

Power calculation

The 2016-2017 in-hospital mortality after major surgery in Nova Scotia is 1.7% (47). Using the Events Per Variable criterion (EPV) of at least 10 outcomes per predictor in the sample, the 1.7% mortality (408) out of an estimated sample size of 24,000 for the derivation/training group means that our model would be valid for up to 41 predictors for the primary outcome. However, the EPV may over or underestimate the limitations of the EPV criterion (48), square root of the mean squared prediction error (rMPSE) and mean absolute prediction error (MAPE) will be calculated based on the number of predictors, sample size and events fraction (49) with the caveat that this model has not been externally validated. Full power calculation will be performed once we receive the final sample size.

Strengths

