CIHI DAD	CCI: Charleson Comorbidity Index [Derived by HDNS]	Patient	Jan 1, 2010 to Dec 31, 2017 (3 years before and including 30 days after date of surgery)	
To be computed by the HDNS according to protocol (33) using DXCODES (please see above), to be included into model as covariate.
 
Please report both total score, and any of the following individual categories:
 
 Myocardial infarction Congestive heart failure Peripheral vascular disease Cerebrovascular disease Dementia Chronic pulmonary disease Rheumatic disease Mild liver disease Moderate or severe liver disease Diabetes without chronic complication Diabetes with chronic complication Hemiplegia or paraplegia Renal disease Any malignancy, including lymphoma and leukemia, except malignant neoplasm of skin Metastatic solid tumor Peptic Ulcer Disease Excluding Bleeding AIDS/HIV
CIHI DAD	RCRI: Revised Cardiac Risk Index [Derived by HDNS]	Patient	Jan 1, 2010 to Dec 1, 2017 (3 years before and including date of surgery)	As RCRI has been shown to affect outcomes (29), it will be included as a covariate. This is based on DXCODE ICD codes (identified above) of history of ischemic heart disease, congestive heart failure, cerebrovascular disease, diabetes on insulin, chronic kidney disease creatinine >176.8 µmol/L, and a list of Canadian Classification of Health Interventions (CCI codes) of

				
suprainguinal vascular, intraperitoneal, or intrathoracic surgery (30).
 
Detailed protocol will be sent to the HDNS. Please provide both the names of the categories and the total score (i.e. for each patient, positive for any of the categories of cerebrovascular disease, ischemic heart disease, congestive heart failure, chronic kidney disease, diabetes, and diabetes on insulin; as well as the total RCRI score (1 point for each positive category).

CIHI DAD	High risk surgery as per RCRI: Suprainguinal vascular, intraperitoneal, or intrathoracic surgery [Flag - Derived by HDNS]	Patient	3 years before and including date of surgery (i.e. Jan 1, 2010 to Dec 1, 2017)	Binary variable (yes/no) As this may affect outcomes, it will be included as a covariate by itself and as part of the Revised Cardiac Risk Index (RCRI) score calculation.

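### The RCRI row in Appendix 1 contradicts itself on diabetes: read literally, its point rule gives every diabetic patient one point more than the plan's own definition of the score

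*Combined protocol and SAP*

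**What the plan says.** The RCRI row of Appendix 1 (Summary of Variables) does two things in one cell.

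- **It defines the score.** The clinical items are "history of ischemic heart disease, congestive heart failure, cerebrovascular disease, diabetes on insulin, chronic kidney disease creatinine >176.8 µmol/L". To these it adds a list of intervention codes for "suprainguinal vascular, intraperitoneal, or intrathoracic surgery (30". That makes six items, with one diabetes item, restricted to insulin treatment.
- **It instructs the data custodian (HDNS).** HDNS is to return, for each patient, whether the patient is "positive for any of the categories of cerebrovascular disease, ischemic heart disease, congestive heart failure, chronic kidney disease, diabetes, and diabetes on insulin". This category list also has six entries, but two concern diabetes and none concerns surgery. The point rule is attached directly to that list, and reads "as well as the total RCRI score (1 point for each positive category".

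The next row, for high-risk surgery, says of that flag that "it will be included as a covariate by itself and as part of the Revised Cardiac Risk Index (RCRI) score calculation". The row for preoperative insulin use says the variable is collected to identify insulin users for the RCRI.

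Table 2 (Other predictors) lists the components as "history of ischemic heart disease, congestive heart failure, cerebrovascular disease, diabetes, chronic kidney disease", followed by the surgery codes. Diabetes carries no insulin qualifier there.

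The score is used twice. In Table 2 it is one of several comorbidity measures from which the most significant is to be kept. Under Sensitivity and subgroup analysis, where "Subgroup analysis will be performed based on age, sex, high preoperative risk", RCRI is also a named subgroup factor.

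**The concern.** A patient with insulin-treated diabetes necessarily has diabetes, so is positive for both "chronic kidney disease, diabetes, and diabetes on insulin" entries that mention it. A rule of one point per positive category then counts one condition twice and also gives a point to diabetes without insulin, which the defining sentence does not score. Table 2 adds a third possibility, in which any diabetes earns one point.

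Two programmers working from the same pages could therefore deliver different totals. The total competes with ASA class, Elixhauser, Charlson and the frailty score for a place in the model. It also forms a subgroup, and if it is the measure retained, it defines the high-preoperative-risk subgroup as well. HDNS does the derivation, and the Appendix says the full set of diagnosis codes need not be disclosed to the research team, so the written instruction carries real weight.

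**Working it through.** The plan states no RCRI range or distribution, so there is no figure to reproduce. The check compares the scores that the different passages produce, using only the documents' own definitions.

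**Notation.** Let b be the sum of the four undisputed items (ischemic heart disease, congestive heart failure, cerebrovascular disease, chronic kidney disease), so b runs 0–4. Let D = 1 for any diabetes, I = 1 for diabetes on insulin (so I = 1 implies D = 1), and S = 1 for high-risk surgery.

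| Reading | Source | Formula | Range |
|---|---|---|---|
| A | Defining sentence of the RCRI row | b + I + S | 0 to 4+1+1 = 6 |
| C | Category list, plus surgery as the next row requires | b + D + I + S | 0 to 4+1+1+1 = 7 |
| B | Category list alone | b + D + I | 0 to 4+1+1 = 6 |
| T | Table 2 components, one point each | b + D + S | 0 to 4+1+1 = 6 |

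**Differences from the defining sentence.**

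- C − A = D. Every diabetic patient gains one point: insulin-treated 2 instead of 1, not insulin-treated 1 instead of 0. Non-diabetic patients do not change.
- T − A = D − I. Only diabetic patients not on insulin gain a point.
- B − A = D − S. This is +1 for diabetic patients without high-risk surgery, 0 for diabetic patients with it, −1 for non-diabetic patients with it, and 0 for the rest.

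**Enumeration.** There are 2⁴ × 3 × 2 = 96 profiles (four binary items, three diabetes states, surgery yes or no). C differs from A in 64 of them, always by +1. B differs from A in 48. These count profiles, not patients, and say nothing about frequency.

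**Which reading the plan means.** The insulin-use row exists to identify insulin users for the score, which fits A. Under C, insulin use would add a second diabetes point. Under T it would have no role. On surgery, the defining sentence, the next row and Table 2 all include it; only the category list does not. The documents as a whole therefore point to A, while the sentence that carries the point rule does not deliver A.

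**Detectability.** A total of 7 would expose reading C, but only in a patient positive on every item. Readings B and T share the 0–6 range of A, so a range check would not find them.

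**The case against.** The strongest defence is that the list names the flags to return and does not define the scored set. The request asks for category names as well as the total, plain diabetes is a reasonable flag to want, and the cell says a detailed protocol will go to HDNS. Table 2 also refers to published methods and may simply be naming components. On this view double scoring is a risk of loose wording.

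Part of this stands. It cannot be said from these documents that the delivered score will be wrong. But the point rule is attached to the listed categories, nothing marks diabetes as unscored, and a protocol that is not in the documents does not resolve a conflict in them.

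The defence is also right that the consequence is bounded. RCRI is one of several candidate measures, its components are delivered separately, and neither the primary outcome nor the hemodynamic exposures depend on it.

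A reader might infer more in three ways that the documents do not support:

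- **That high-risk surgery scores zero.** It is absent from the category list, but the defining sentence, the next row and Table 2 all put it in the score. The absence fits its being requested as its own flag.
- **That patients move up or down an RCRI class.** The plan names RCRI as a subgroup factor but gives no classes or cut-points.
- **That a count of mis-scored patients can be given.** No diabetes prevalence is stated, so any count would only restate an assumed prevalence multiplied by the estimated 35,000 patients. If surgery were also dropped, the two errors would cancel in diabetic patients having high-risk surgery.

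**Conclusion.** The scoring of diabetes in the RCRI is inconsistently specified and should be corrected. Measured against the plan's own defining sentence, the literal point rule with surgery scored adds exactly one point for every diabetic patient, changes no one else, and stretches the range from 0–6 to 0–7. The Table 2 version would add a point only for diabetic patients not on insulin. The number of patients affected, and any effect on model selection or subgroup results, cannot be derived from the documents.

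The missing surgery item is a wording gap to close in the same edit. The conclusion rests on taking the defining sentence as the intended score, which the insulin-use row and the high-risk surgery row support. It does not rely on the publication cited for the index.

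**What to change.** In the RCRI row, replace the category list and point rule with one scored list that matches the defining sentence: one point each for ischemic heart disease, congestive heart failure, cerebrovascular disease, diabetes on insulin, creatinine above 176.8 µmol/L, and high-risk surgery, for a total of 0–6. State that plain diabetes is returned as a separate flag and does not enter the total. Add the insulin qualifier to the RCRI components in Table 2, and check that the detailed protocol sent to HDNS uses the same list.

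The cost is one line in the derivation and a small edit to Table 2. Insulin use, creatinine, the diagnosis categories and the surgery flag are all already requested. If the score has already been delivered, the team can recompute it from the component flags and compare it with the supplied total.
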